***3. TC Training Sessions the Tele-TC Platform (12 weeks)***

Study volunteers will participate in a 12-week simplified TC program that we have used in multiple prior clinical studies. In this pilot study, the intervention will be delivered via our platform-based application. All participants will be provided with a tablet with the Tele-TC software installed. The structured intervention, designed for older adults, emphasizes essential TC movements that are easily comprehensible and can be performed repetitively in a flowing manner. The protocol includes up to six core TC movements based on the traditional Cheng Man-Ch'ing's Yang-style short form. Additionally, a complementary set of traditional TC warm-up exercises that focus on loosening the physical body, incorporating mindfulness and imagery into movement, promoting overall relaxation, and coordinating breathing awareness are included. Chairs are used in the protocol for a subset of seated warm-up exercises, as well as for stability and rest as needed. Participants will be asked to practice the protocol (45-60 min) at home for at least 3 days a week for 12 weeks. In addition to data on practice frequency, duration, protocol adherence and training proficiency being automatically collected through our platform, a weekly REDcap survey will be used to monitor adverse events. The TC program will also include 2 or more live instructional sessions via Zoom with a TC instructor.

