## **1. Background and Significance**

Non-pharmacological early-intervention strategies to slow the growing epidemic of age-related cognitive decline and dementia, and their well-established impact on functional outcomes, must include the targeting of executive function (EF). EF encompasses several essential higher cognitive skills, including attentional control, planning, response inhibition and working memory. In addition to portending Alzheimer's disease, executive dysfunction in older adults is associated with impaired gait and balance and higher fall risk, which significantly decrease functional independence and overall quality of life (QOL).

Exercise is considered a promising intervention for preservation and restoration of cognitive function in older adults, including EF, with literature reviews suggesting that multimodal training that integrates physical and cognitive training may have advantages over unimodal interventions. Tai Chi (TC) is an increasingly popular multimodal mind-body exercise that incorporates physical, cognitive, social, and meditative components within the same activity. Recent meta-analyses show that TC is a promising intervention for EF and global cognitive function in older adults. In several studies, TC was found to be superior to conventional exercise.

The CDC and many other agencies endorse TC. Yet surprisingly, a comprehensive 2014 national survey found that only 1.2% of the entire adult population reported using TC for health, suggesting potential limitations in access to training programs. Limited access to community training programs is also indicated by the fact that a significant percentage of survey respondents reported learning TC from online or video courses.

During phase I of the SBIR NIH grant, we developed algorithms based on information gathered from wearable sensors to estimate adherence, proficiency, and safety metrics. During the non-clinical stages of phase II, we developed a complete beta-version of the Tele-TC platform. The Tele-TC system consists of a set of 5 wearable sensors and an app installed on a commercially available tablet.

As a preliminary step toward designing a future study to assess the clinical benefits of the Tele-TC platform as a training system for elderly with mild cognitive impairments, we herein propose to assess:

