- If the system enables monitoring longitudinally of adherence, proficiency, and safety.
- If the system is acceptable and user-friendly for its intended use in the home setting.
- As an exploratory aim: if a 12-week training program using the Tele-TC platform leads to improvements in cognitive function, balance, physical activity, self-efficacy, health-related quality of life, and gait.

If this preliminary study leads to positive results, we will embark on a follow-up study to assess the potential clinical benefits of using the technology as part of a clinical intervention on cognition, balance, physical activity, gait, self-efficacy, and health-related quality of life.

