### Primary aims

- Aim 1: *To evaluate the feasibility, acceptability, and safety of a novel home-based Tele-TC intervention by tracking recruitment, retention, adherence, and adverse events.*
  - Hypothesis 1: We will be able to recruit 20 older adults with mild cognitive impairment and limit withdrawals to 20% or less.
  - Hypothesis 2: Participants will complete >60% of recommended Tele-TC sessions.
  - Hypothesis 3: Protocols for assessing safety can be developed and reliably administered, and preliminary evidence will support Tele-TC can be delivered safely.

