- Participants will be instrumented with 5 sensors (one on each limb and one on the trunk) and they will be following the instructions from the Tele-TC platform.

Study staff will use Zoom to communicate with subjects during the visits done remotely. The performance of TC exercises will also be videorecorded and scored using the proficiency metric described in our preliminary studies section to provide a gold standard. We will try to use the sensors during the remote visits, but if it is not possible, we will document the reasons and continue the TC exercises only with video.

Subjects will be asked to don one Smart GeneActiv watch by ActivInsights\* on their wrist to monitor activity during approximately a week after visits #1B and a week before visit #4.

We will ask the participants to send the GeneActiv back to the lab after wearing it. We will be sending another GeneActiv about two weeks before visit #4.

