***4. Remote Monitoring of Falls and Other Adverse Events***

We will monitor falls during the subject's participation in the intervention study. Falls will be defined as any event in which the participant unintentionally comes to rest on the ground or other lower level, not as a result of a major intrinsic event or an overwhelmingly external hazard. Falls will be systematically monitored in two ways. As part of our safety and adverse events (AE) monitoring, participants will be asked to complete a weekly REDcap adverse events survey about their TC practice and activities of daily living. Study staff will follow-up by phone with participants as necessary. During study visits #1b-#4, study personnel will inquire about and record characteristics and details of falls and other adverse events.

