## ***7. Data variables analysis to be collected***

The primary outcomes of the study are the retention and the protocol adherence during the study, and the System Usability Scale collected post-intervention.

The exploratory outcomes will include the following:

- The ease of use of the Tele-Tai Chi platform measure with the qualitative interview collected post intervention.
- The changes in outcomes collected at baseline and post-intervention: the Activities-specific Balance Confidence (ABC) scores, PROMIS 29 scores, the Physical Activity Scale for the Elderly (PASE), the Trail Making Test A/B scores, Self-Efficacy Exercise (SEE) scores, the grip strength, the Controlled Oral Word Association Test (COWAT), the Digit Span Test, the Timed-Up-and-Go, the Timed-Up-and-Go dual task single leg stance, the Sit-to-Stand performance, the balance on both legs with feet shoulder-width apart, the balance on both legs with feet close to each other, the normalized-to-height stride length and stride time variability, the activity level, and the Mini-Balance Evaluation Systems Test (MiniBEST) collected only in individuals who are willing to be tested in the MAL.
- The changes in The Tai Chi proficiency scores collected at baseline, 4 weeks, 8 weeks, and post-intervention.

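### Adherence is taken only from the platform whose ability to monitor adherence is being assessed, so an unlogged home session cannot be told apart from a missed one

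*Combined protocol and SAP*

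**What the plan says.** Section 1 (Background and Significance) gives as one item to assess "If the system enables monitoring longitudinally of adherence, proficiency, and safety". It also defines the platform: "The Tele-TC system consists of a set of 5 wearable sensors and an app installed on a commercially available tablet". A sensor-based measure of adherence is therefore a measure from the system under assessment.

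Under Primary aims, Hypothesis 2 of Aim 1 reads "Participants will complete >60% of recommended Tele-TC sessions". Section 6.7 makes adherence primary: "The primary outcomes of the study are the retention and the protocol adherence during the study", together with the System Usability Scale. Section 6.3 asks for practice "at home for at least 3 days a week for 12 weeks" and describes "data on practice frequency, duration, protocol adherence and training proficiency being automatically collected through our platform". Section 9 (Statistical Analysis) relates sensor-based adherence estimates to clinical outcomes.

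The weekly survey is assigned to adverse events in Section 6.3. Section 6.4 describes it as a "weekly REDcap adverse events survey about their TC practice and activities of daily living". For the remote visits, Section 6.2 says "We will try to use the sensors during the remote visits, but if it is not possible, we will document the reasons".

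**The concern.** When a device is both the thing being assessed and the only measure of the outcome, its failures are hidden inside that outcome. If a participant practises and the platform records nothing, the log shows a gap. If the participant does not practise, the log shows the same gap. The plan names no other record that would separate the two.

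Two results depend on the difference. One is the question of whether the system can monitor adherence, where gaps in capture are the quantity of interest. The other is the adherence criterion of more than 60%. A shortfall there could come from a technical fault or from a programme that people do not keep up, and these call for different changes before the next study.

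**Working it through.** The plan gives no capture rate and no sample-size or power figure, so there is nothing of its own to reproduce. The check has two parts.

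**1. Is any second record of home sessions assigned to adherence?**

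| Source | Where | What it covers | Tied to adherence? |
|---|---|---|---|
| Platform (app and five sensors) | 6.3, 9 | Home sessions | Yes, the only one |
| Weekly REDCap survey | 6.3, 6.4 | Adverse events; touches on practice | No session count stated |
| Video recording | 6.2 | Proficiency reference at visits | No; home practice not covered |
| GeneActiv wrist watch | 6.2 | General activity, about one week at each end of the 12 weeks | No |
| Exit interview, System Usability Scale | 6.5 | Usability at study end | No |
| Reasons for not using sensors | 6.2 | Remote visits | No; home practice not covered |

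Proficiency is given an independent reference (scored video). Adherence is given none, although the same Background bullet names both.

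**2. What could incomplete capture do?** Every capture rate and true-adherence value below is an assumption.

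*Group level.* Expected logged adherence = true adherence × capture, where capture is the share of practised sessions that are logged.

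- True 70%: 0.70 × 0.90 = 63%; 0.70 × 0.80 = 56%; 0.70 × 0.70 = 49%. Break-even capture is 0.60 / 0.70 = 85.7%.
- True 80%: 0.80 × 0.90 = 72%; 0.80 × 0.80 = 64%; 0.80 × 0.70 = 56%. Break-even capture is 0.60 / 0.80 = 75%.

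The criterion is more than 60%, so it is missed at or below break-even.

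*Participant level.* The minimum recommendation is 3 × 12 = 36 sessions, counting one session per recommended day. Since 0.60 × 36 = 21.6, at least 22 must be logged (22/36 = 61.1%). For someone who practised 26 (26/36 = 72%), with each session lost independently with probability f, the chance of reaching the criterion is P(X ≥ 22), where X ~ Binomial(26, 1 − f):

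| Assumed loss f | 5% | 10% | 20% | 30% |
|---|---|---|---|---|
| P(at least 22 logged) | 0.99 | 0.89 | 0.38 | 0.07 |

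The plan does not say whether the 60% applies to each participant or to the group mean, so both are shown.

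*Reading the log backwards.* With losses anywhere from 0% to 30%, a logged 50% is compatible with true adherence from 0.50 / 1.00 = 50% to 0.50 / 0.70 = 71%. That range lies on both sides of the criterion, and the log alone cannot narrow it.

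**The case against.** Several points on the other side have force.

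- **The survey may already ask.** Section 6.4 says it concerns Tai Chi practice, and staff follow up by phone as necessary. The form is not in the documents. This stands: one cannot say the survey ignores practice, only that no session count and no link to the log are stated.
- **Sensor failure need not lose the session.** A reader might infer that a session without working sensors is scored as non-adherent. No such rule is written. The app delivers the session and could log it without sensor data. The gap is that the plan does not say which applies.
- **The remote-visit sentence is weak evidence.** It gives no failure rate and concerns visits run over Zoom. It shows that the plan foresees sensor problems, not how common they will be at home.
- **The monitoring question is a Background bullet.** The formal Aim 1 concerns feasibility, acceptability and safety. A reader might infer that the question cannot be answered at all. That goes too far: usable logs over 12 weeks would partly answer it, and the adherence algorithms come from earlier work that cannot be judged here.
- **Practice away from the platform may rightly not count**, because Hypothesis 2 concerns Tele-TC sessions. This stands, and is a reason to keep the logged figure as primary.
- **This is a descriptive pilot of 20 people.** That limits the consequences. But the study exists to inform later trials, and unrecorded sessions are hard to reconstruct afterwards.

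None of this supplies a comparison of logged with practised home sessions.

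**Conclusion.** The point holds in a limited form. As written, the plan takes a primary outcome from the system whose monitoring it wants to assess, and names no means of separating an unlogged home session from a missed one. Logged adherence may therefore understate practice.

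The size is unknown. The break-even capture rates of about 86% and 75% rest on assumed true adherence of 70% and 80%. The participant-level figures also assume independent losses and no over-logging. They show that moderate loss could decide whether the criterion is met, not that such loss will occur. The documents do not support a claim that the adherence result will be wrong. This is an inexpensive improvement to make before data are collected, not a flaw that invalidates the study.

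**What to change.** **In the existing weekly REDCap survey**, ask for:

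- the number of Tai Chi sessions practised that week;
- how many were done with the app, and how many with the sensors;
- the reason whenever either was not used or failed.

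If the survey already asks this, use those answers.

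**In the analysis plan:**

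- keep platform-logged adherence as the primary figure;
- state whether an app-logged session without sensor data counts, and whether the 60% applies per participant or to the group;
- report weekly agreement between logged and self-reported practice, both counted in sessions, with counts of technical failures;
- add a sensitivity adherence figure that includes sessions reported but not logged.

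**Cost:** a few items in a survey already sent, and one extra table. No new visit or device is needed.

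**Downside:** self-report in people with mild cognitive impairment can err in either direction. The second figure is therefore a sensitivity analysis and not a strict upper bound, and the agreement result is supporting evidence on monitoring, not a validation of the log.

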***4. Remote Monitoring of Falls and Other Adverse Events***

We will monitor falls during the subject's participation in the intervention study. Falls will be defined as any event in which the participant unintentionally comes to rest on the ground or other lower level, not as a result of a major intrinsic event or an overwhelmingly external hazard. Falls will be systematically monitored in two ways. As part of our safety and adverse events (AE) monitoring, participants will be asked to complete a weekly REDcap adverse events survey about their TC practice and activities of daily living. Study staff will follow-up by phone with participants as necessary. During study visits #1b-#4, study personnel will inquire about and record characteristics and details of falls and other adverse events.

***5. Feedback from the Subjects***

During the last visit (visit #4), we will conduct a semi-structured qualitative interview to gather feedback from the subjects regarding the feasibility and acceptability of the study overall, and more specifically the usability of the Tele-TC platform. We will ask them to provide us with feedback regarding general characteristics of the platform, possible improvements of the system, and whether they would consider using the system on a daily basis at home. The qualitative interview will be audio recorded. In addition, at the end of the study, we will use an adapted version of the System Usability Scale (SUS).

## ***6. Return of devices***

The subjects will be asked to return the devices (mobile devices, sensors, tablet stands) during visit#4. The final payment for the study (\$70) will be contingent on the return of the study equipment.

## ***7. Data variables analysis to be collected***

The primary outcomes of the study are the retention and the protocol adherence during the study, and the System Usability Scale collected post-intervention.

The exploratory outcomes will include the following:

- The ease of use of the Tele-Tai Chi platform measure with the qualitative interview collected post intervention.
- The changes in outcomes collected at baseline and post-intervention: the Activities-specific Balance Confidence (ABC) scores, PROMIS 29 scores, the Physical Activity Scale for the Elderly (PASE), the Trail Making Test A/B scores, Self-Efficacy Exercise (SEE) scores, the grip strength, the Controlled Oral Word Association Test (COWAT), the Digit Span Test, the Timed-Up-and-Go, the Timed-Up-and-Go dual task single leg stance, the Sit-to-Stand performance, the balance on both legs with feet shoulder-width apart, the balance on both legs with feet close to each other, the normalized-to-height stride length and stride time variability, the activity level, and the Mini-Balance Evaluation Systems Test (MiniBEST) collected only in individuals who are willing to be tested in the MAL.
- The changes in The Tai Chi proficiency scores collected at baseline, 4 weeks, 8 weeks, and post-intervention.

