When - according to a rehabilitation specialist during in-person testing, or research staff during virtual testing - subjects are unable to safely perform the TC exercises that are part of the experimental procedures, the experiment will end. Subjects will be told why the experiment must stop and will be advised to seek medical care if appropriate.

Subjects will be told that the study procedures may be associated with discomfort due to wearing the sensors and by fatigue/muscle soreness. In case subjects experience discomfort or excessive fatigue, they will be free to remove the sensors and end their participation in the study.

Unintentional loss/disclosure of Protected Health Information may occur and is considered a minimal risk due to the security measures enforced at SRH. Confidential information will be kept in a locked filing cabinet, on REDcap, and on password-protected computers in the MAL.

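### The System Usability Scale, a primary outcome, is collected only at the end of the study, so the usability result describes those who reach the final assessment and leaves out participants who withdraw

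*Combined protocol and SAP*

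**What the plan says.** Section 6, item 7 lists the primary outcomes: "The primary outcomes of the study are the retention and the protocol adherence during the study, and the System Usability Scale collected post-intervention". Section 6, item 5 gives the only time point for the scale: "at the end of the study, we will use an adapted version of the System Usability Scale (SUS"). That sentence closes a paragraph about the visit #4 interview, which covers the "feasibility and acceptability of the study overall, and more specifically the usability of the Tele-TC platform".

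Section 2, Hypothesis 1 under Aim 1, expects 20 participants and sets 20% as the acceptable limit for withdrawals. Section 7 tells participants that the procedures may bring "discomfort due to wearing the sensors and by fatigue/muscle soreness", and continues: "In case subjects experience discomfort or excessive fatigue, they will be free to remove the sensors and end their participation in the study".

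Some information on people who leave is collected. Section 6, item 3 describes "data on practice frequency, duration, protocol adherence and training proficiency being automatically collected through our platform" and adds that "a weekly REDcap survey will be used to monitor adverse events". Section 6, item 4 says: "Study staff will follow-up by phone with participants as necessary".

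Section 9 plans descriptive statistics for the clinical assessments. It names no SUS analysis, no analysis set and no handling of missing scores.

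**The concern.** A usability score is most informative when it includes people who gave up on the system. Here the scale is tied to the end of the study, and the visible text has no rating at withdrawal. A participant who leaves in week 3 contributes to retention and, up to that point, to adherence and adverse-event data. None of these says how that person rated the platform.

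The missing ratings may not be a random subset. Section 7 allows exit for discomfort, which it attributes both to the sensors and to fatigue or muscle soreness. Some withdrawals may therefore be related to the system being rated, and others not.

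What is at stake is interpretation. Section 1 asks whether the system is acceptable and user-friendly at home, and makes a follow-up study conditional on positive results. A score from those who stayed answers a narrower question than that.

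**Working it through.** The plan gives no SUS data and no sample-size calculation, so there is no stated figure to reproduce. What follows are scenarios.

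**Inputs from the plan.** N = 20. Withdrawal limit 20%: 20 × 0.20 = 4 withdrawn, leaving 16 rated. Four is a hypothesis, not a cap. The binomial chance of 4 or fewer withdrawals in 20 is 0.96, 0.63 and 0.24 if the true rate is 10%, 20% and 30%.

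**Assumptions, not in the plan.** The adapted SUS is scored 0-100 and summarised as a mean; SD 15 to 20; mean of 70 among those rated.

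**Step 1: overstatement.** With w withdrawn, the all-enrolled mean is [(20 − w) × mean of those rated + w × mean of withdrawers] / 20. Hence

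overstatement = (w/20) × gap,

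where gap = mean of those rated minus mean of withdrawers.

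| Withdrawn | Gap 0 | Gap 10 | Gap 20 | Gap 40 |
|---|---|---|---|---|
| 2 | 0 | 1 | 2 | 4 |
| 4 | 0 | 2 | 4 | 8 |
| 6 (limit exceeded) | 0 | 3 | 6 | 12 |

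**Step 2: comparison with sampling error.** 95% half-width = t(0.975, n − 1) × SD/√n. For n = 16: 2.131 × 15/4 = 7.99 and 2.131 × 20/4 = 10.66. The gap at which overstatement equals the half-width is half-width / (w/20).

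| Withdrawn | Rated | Half-width (SD 15 / 20) | Gap needed (SD 15 / 20) |
|---|---|---|---|
| 2 | 18 | 7.46 / 9.95 | 74.6 / 99.5 |
| 4 | 16 | 7.99 / 10.66 | 40.0 / 53.3 |
| 6 | 14 | 8.66 / 11.55 | 28.9 / 38.5 |

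With 2 withdrawn and a mean of 70 among those rated, the gap cannot exceed 70, so the overstatement cannot reach the half-width.

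**Step 3: bounds without assuming a gap.** Give every withdrawer 0, then 100, with a mean of 70 among those rated.

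- 2 missing: 18 × 70/20 = 63 to (1260 + 200)/20 = 73
- 4 missing: 16 × 70/20 = 56 to (1120 + 400)/20 = 76
- 6 missing: 14 × 70/20 = 49 to (980 + 600)/20 = 79

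The largest possible overstatement is therefore 7, 14 or 21 points, and it requires every withdrawer to score 0.

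**The case against.** The main objections, and what stands of each:

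- **The restriction is inferred from silence.** The end of the study could mean the end of each person's participation, and the flow chart is not visible in the text reviewed. This stands as a caution. However, item 7 places the scale after the intervention and item 5 pairs it with visit #4, and both favour the narrower reading. If the other was meant, one sentence settles it.
- **The rated group is wider than adherent users.** A reader might infer that only those who followed the programme are rated. The documents do not say so: someone who stopped practising but attends the last assessment is still rated. Section 6, item 6 also makes the final payment contingent on return of the equipment, which is due at visit #4, so disengaged participants have a reason to come. This stands in full.
- **Retention is itself primary.** The share lost will be visible beside the SUS. That warns the reader that ratings are missing, but does not show what they would have been.
- **The effect is probably small.** With 4 withdrawn and a 20-point gap, the shift is 4 points against a half-width of about 8 to 11. This stands for modest gaps. A confidence interval would not reveal the bias, however, and the plan does not promise an interval.
- **A score after 12 weeks is a legitimate target.** Exit scores reflect shorter exposure, so pooling mixes two quantities. This stands, and is why the post-intervention score should remain the main summary.

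**Conclusion.** The concern holds as a minor point. Read as written, the plan yields a usability result for those who reach the final assessment, with no rating from those who withdraw. At 4 withdrawals the possible overstatement is 2 points per 10-point gap. It stays below sampling error unless the gap is about 40 points (SD 15) to 53 points (SD 20). These figures rest on the assumed 0-100 scoring, use of a mean, and assumed SD.

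Two stronger readings are tempting. One is that the SUS result will be biased upward. The documents do not support this: upward bias requires that withdrawers would rate the platform lower, and Section 7 links discomfort to fatigue and soreness as well as to the sensors. The other is that a trial conclusion is invalidated. The plan states no SUS threshold, hypothesis or test, so interpretation is affected and no formal decision is.

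A reader may also notice that the outcome lists in Section 2 and Section 6, item 7 differ, and that scoring of the adapted scale is not described. Those are separate wording matters and not part of this conclusion.

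**What to change.** Add to Section 6, item 5 that a participant who withdraws will be sent the adapted SUS by REDCap email link at that time, and that the reason for withdrawal will be recorded. Keep the post-intervention SUS as the main summary. Report with it:

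- the number rated out of all enrolled;
- a sensitivity summary that includes withdrawal scores, labelled as reflecting shorter exposure;
- best- and worst-case bounds for ratings still missing.

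Partial response already helps. With 4 withdrawn and a mean of 70 among the other 16, suppose 2 withdrawers reply with an assumed mean of 50. The bounds become (1120 + 100 + 0)/20 = 61 to (1120 + 100 + 200)/20 = 71, a width of 10 points instead of 20.

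The cost is a few lines of protocol text and one short questionnaire. REDCap email links already deliver the study questionnaires, and a working email address is an inclusion criterion. The downsides are that withdrawal scores come from less use of the platform and that some withdrawers will not respond, so the bounds are still needed. The step should be in place before the first withdrawal, since ratings not sought then may not be recoverable.
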